TSH	Thyroid stimulating hormone
UADE	Unanticipated adverse device effect
ULN	Upper limit of normal
US	United States
vBMD	Volumetric bone mineral density
WHO	World Health Organization

PROTOCOL SYNOPSIS

Title: A Randomized, Double-blind, Placebo-controlled, Phase 3 Multicenter Study to Evaluate the Safety and Efficacy of Abaloparatide-SC for the Treatment of Men with Osteoporosis

Protocol Number: BA058-05-019

Test Drug: Abaloparatide 80 µg for subcutaneous injection

Study Objectives and Endpoints

Objective: The primary objective of this prospective controlled study is to evaluate the efficacy and the safety of abaloparatide-subcutaneous (SC) 80 μ g per day compared to placebo in men with osteoporosis.

Endpoints

The primary efficacy endpoint is the percent change from baseline in lumbar spine bone mineral density (BMD) at 12 months.

The key secondary efficacy endpoints are:

- Percent change from baseline in total hip BMD at 12 months
- Percent change from baseline in femoral neck BMD at 12 months

Additional secondary efficacy endpoints are:

- Percent change from baseline in:
 - Lumbar spine BMD at 3 and 6 months
 - Total hip BMD at 3 and 6 months
 - Femoral neck BMD at 3 and 6 months
 - Ultra-distal radius BMD at 3, 6, and 12 months
 - Distal one-third radius BMD at 3, 6, and 12 months
- Log ratio of post-baseline over baseline in:
 - Serum procollagen type I N-terminal propeptide (s-PINP) at 1, 3, 6, and 12 months
 - Serum carboxy-terminal cross-linking telopeptide of type I collagen (s-CTX) at 1, 3, 6, and 12 months
- Proportion of subjects experiencing BMD gains from baseline of > 0%, > 3%, and > 6% at the lumbar spine, femoral neck, and total hip at 3, 6, and 12 months
- Incidence of new clinical fractures at 12 months
- Proportion of subjects converting from the categories of osteoporosis to osteopenia or to normal at 12 months, where:
 - Osteoporosis is defined as lumbar spine or total hip BMD T-score \leq -2.5.

- Osteopenia is defined as one of the following:
 - Lumbar spine > -2.5 and total hip BMD T-score > -2.5 and < -1.0
 - \circ Lumbar spine > -2.5 and < -1.0 and total hip BMD T-score > -2.5
- Normal is defined as lumbar spine and total hip BMD T-score \geq -1.0.
- The percent change in total hip and femoral neck volumetric BMD (vBMD) as measured by quantitative CT (QCT) from baseline to 12 months. QCT will be performed in a subset of subjects at a selected number of study sites.

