The analyses of the key secondary BMD endpoints will be performed using a PMM analysis with multiple imputation using the wash-out imputation method similar to the analysis for the primary efficacy endpoint, as stated in Section 8.4.2, with the appropriate baseline covariate. Sensitivity analyses using MMRM models, sensitivity analyses for addressing the effect of the COVID-19 pandemic, and supportive analyses using the LOCF method, as with the primary efficacy endpoint, will also be conducted.

The bone formation marker, s-PINP, and the bone resorption marker, s-CTX, will be analyzed based on the ratio of the post-baseline value relative to the baseline using a natural log transformation at each visit. The analysis will use a PMM analysis with multiple imputation using the wash-out imputation method similar to that described in Section 8.4.2.
Percent changes from baseline in BMD over time will be summarized using descriptive statistics by visit for each treatment group.

The bone formation marker, s-PINP, and the bone resorption marker, s-CTX, will be summarized descriptively by treatment group, with values, changes and percent changes from baseline, geometric mean values, and geometric mean values relative to baseline at each visit.

A BMD responder analysis by visit will be performed for those subjects who have both baseline and the relevant post-baseline BMD values. Three categories of BMD response will be evaluated: %BMD increase > 0%, > 3%, and > 6%. The response will be assessed at the lumbar spine, total hip, and femoral neck. Subjects who have BMD increase at all 3 skeletal sites at the same visit will be considered responders, with the primary time point at 12 months. No imputation of missing data will be implemented. The number and percentage of responders in each treatment group will be compared using either the Chi-square test or Fisher's exact test.

Kaplan-Meier estimates for the time to new clinical fracture at 12 months and the hazard ratio (99% CI) will be presented, with treatment comparisons based on the log-rank test.

The number and percentage of subjects for whom disease status (categories as defined in the secondary endpoints listed earlier in this section) has changed from osteoporosis at baseline to osteopenia, normal, or no change at 12 months will be analyzed using the Chi-square test.

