8.5. Sample Size Calculation

A study sample size of 225 subjects (150 in the abaloparatide-SC group and 75 in the placebo group) will provide at least 99% power to detect a mean difference of 6.5% in the percentage change from baseline in lumbar spine BMD at 12 months between the abaloparatide-SC and the placebo groups at a 2-sided alpha level of 0.01, assuming a SD of 6.0% and a drop-out rate of 10%. For the key secondary endpoints, this total sample size of 225 subjects will have 96% power to detect a 2.2% mean difference (SD = 3.5%) of percent change in total hip BMD at 12 months, and 80% power to detect a 2.0% mean difference (SD = 4.1%) of percent change in femoral neck BMD at 12 months.

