#### Figure 1: Study BA058-05-019 Study Design

## 1.2.2 Randomization Methodology

It is planned to enroll approximately 225 subjects at up to 40 study sites in 3 to 5 countries to receive either abaloparatide-SC 80  $\mu$ g or placebo in a 2:1 ratio on Day 1 using permuted block randomization.

Study medication kits will be shipped to each study site. Once a subject has been deemed eligible to be randomized into the study on Day 1 (Visit 3), the study site will use the Interactive Response Technology (IRT) system to assign a medication kit to the subject. Throughout the study, medication kits will be assigned to the subject based on information provided by the IRT.

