## 4.3 Efficacy Analyses

The ITT population will be the primary population for all efficacy analyses. The PP population will be used for supportive analyses. In efficacy analyses, subjects will be analyzed according to the treatment to which they were randomized.

The primary and BMD-related secondary efficacy endpoints will be derived from the Bioclinicacorrected BMD measurements.

BMD scans may be deemed unevaluable at the first reading and a repeat BMD scan may be performed. The re-scan BMD assessment will be recorded as an unscheduled visit for the corresponding nominal visit. To determine the assessment that will be used for a given study visit by the analysis window convention, all BMD assessments (including unscheduled BMD assessments) will be considered. In the efficacy analyses by nominal visit, unscheduled BMD assessments will be used if the BMD assessment at the nominal visit is not available but an unscheduled BMD assessment for the same nominal visit is available.

Analyses of the BMD-related efficacy endpoints and the serum markers of bone metabolism (s-PINP and s-CTX) will be conducted using the analysis visit windows defined in Table 4 of Section 3.12 as the primary analysis. Analyses of the BMD-related efficacy endpoints and the serum markers of bone metabolism (s-PINP and s-CTX) using the nominal visits will also be presented as supportive analyses.

All confidence intervals, statistical tests, and p-values will be reported as nominal 2-sided. The primary and key secondary efficacy endpoints will be assessed at the significance level of 0.01. All other efficacy endpoints will be assessed at a significance level of 0.05.

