A BMD responder analysis will be performed for exploratory purposes. This analysis will be based on the ITT population. Three categories of BMD response will be evaluated: % BMD increase >0%, >3%, and >6%. The by-visit responses (using analysis visit windows described in Table 4) will be assessed at the lumbar spine, total hip, and femoral neck. For the "all sites" analysis, subjects who have the pre-specified percentage BMD increase at all three anatomical sites at the same visit will be considered responders. A subject must have non-missing BMD results at all three sites at the same visit to be included in the "all sites" analysis. No imputation of missing data will be implemented. For the "all sites" analysis, the BMD response status at end of study will also be summarized. In this analysis, the "all sites" response status will be based on the subject's last BMD assessment during the study. If the last BMD assessment is missing the result for one or two anatomical site(s), the subject will be classified as a non-responder at End of Study. The denominator for the percentage of BMD responders at End of Study will be the number of subjects in the ITT population who had both a baseline and a post-baseline BMD.

BMD responder analyses will also be performed at each of the three anatomical sites separately, using the same three categories of BMD response used in the "all sites" analysis. A subject must have non-missing BMD results at a given visit to be included in the by-visit analysis. No imputation of missing BMD data will be implemented.

The primary time point for all BMD responder analyses is Month 12. The chi-square test will be used to explore the difference in the number (%) of responders between the two treatment groups at each visit (Months 3, 6 and 12) for each category of response. If the number of responders is less than five in any treatment group, the Fisher's exact test will be used. No multiplicity adjustment to the p-values for the BMD responder analysis will be implemented.

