Analysis of the time to new clinical fracture during the study will be performed for exploratory purposes. Duration in days from the date of randomization to the first incidence of clinical fracture will be derived. The crude incidence rates of new clinical fracture, Kaplan-Meier estimates of the incidence rate at Month 12, hazard ratio (95% CI) based on a Cox proportional hazard model, Kaplan-Meier curves, and p-values from the log-rank test for the comparison of the treatment groups will be generated using the ITT and PP populations for this time-to-event variable. If a subject does not experience any clinical fracture over the 12 months of treatment plus the 30-day follow-up, this subject will be censored at the last known day in the study up to the follow-up visit.

The number and percentage of subjects for whom disease status has changed from osteoporosis at baseline to osteopenia or to normal (Refer to Section 4.3.2 for the definitions of osteoporosis, osteopenia, and normal), or no change at end of treatment will be tabulated; and will be analyzed using the Cochran-Mantel-Haenszel (CMH) test stratified by baseline disease status for the ITT population. No imputation of missing BMD data will be implemented.

The percent change from baseline in total hip and femoral neck volumetric BMD (vBMD) at Month 12, as measured by quantitative computed tomography (QCT), will be analyzed using an ANCOVA model with fixed effects of treatment and DXA instrument manufacturer, and with the relevant vBMD baseline value as covariate for the ITT population. No imputation of missing vBMD data will be implemented.

Study BA058-05-019 SAP

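### The exploratory new-clinical-fracture analysis relies on a large-sample log-rank p-value and a Cox hazard ratio, with no rule for small counts or for an arm without fractures

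*Protocol*

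**What the plan says.** The Protocol (Synopsis, Sections 2.2 and 8.4.3) lists "Incidence of new clinical fractures at 12 months" among the additional secondary efficacy endpoints. For the analysis, Protocol 8.4.3 plans Kaplan-Meier estimates and says that the "hazard ratio (99% CI) will be presented, with treatment comparisons based on the log-rank test".

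SAP 4.3.2, under the additional secondary endpoints, labels the time-to-fracture analysis exploratory. It plans crude incidence rates, the Kaplan-Meier incidence at Month 12, and a "hazard ratio (95% CI) based on a Cox proportional hazard model, Kaplan-Meier curves, and p-values from the log-rank test". Men without a fracture are censored at their last known day, up to the follow-up visit.

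On the error level, SAP 4.3 states: "All other efficacy endpoints will be assessed at a significance level of 0.05". Protocol 8.1 sets 1% as the default. SAP 3.7 and Protocol 8.4.3 both place fractures outside the three-step fixed sequence, with supportive p-values and no multiplicity adjustment.

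Neither document gives an exact test, a minimum number of events, or an instruction for an arm with no fracture. The same SAP section does provide for sparse data in the BMD responder analysis: "If the number of responders is less than five in any treatment group, the Fisher's exact test will be used".

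**The concern.** The log-rank p-value comes from a normal approximation that needs a reasonable number of events. With 150 men on drug and 75 on placebo followed for about a year, the count may be small.

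Allocation of 2:1 makes the approximation lopsided. Under no effect, each fracture has about a one in three chance of falling in the placebo arm, so a few placebo fractures give a large z. The same number on drug gives a much smaller one. The Cox estimate fails altogether when one arm has no event.

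What is at stake is how an exploratory result reads. The report could print p<0.05 for a fracture benefit resting on two events, beside a hazard ratio of zero with no usable interval.

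**Working it through.** **Inputs.** The arms are 150 and 75 (Protocol 8.5), randomised "in a 2:1 ratio on Day 1" (SAP 1.2.2). The two-sided level is 0.05 (SAP 4.3). The documents state no fracture rate, event count or power for this endpoint, so there is no planned figure to reproduce. Assumed 12-month risks of 1%, 2% and 3%, equal in both arms, give 225 × risk = 2.25, 4.5 and 6.75 expected fractures.

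**Log-rank p for 2 placebo fractures and none on drug.** The statistic is z = (O − E)/√V, with each man leaving the risk set at his event.

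- E = 75/225 + 74/224 = 0.3333 + 0.3304 = 0.6637, so O − E = 1.336.
- V = 0.3333 × 0.6667 + 0.3304 × 0.6696 = 0.2222 + 0.2212 = 0.4434.
- z = 1.336/√0.4434 = 2.007, so p = 0.0448.

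**Exact p for the same split.** With two fractures in total, the chances of 0, 1 or 2 in the placebo arm are 0.443, 0.446 and 0.110, the last being (75/225) × (74/224). The 2-0 split is the least likely outcome, so the two-sided p is 0.110. Taking 10% off each arm (135:68) gives 0.0455 against 0.111.

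**Other splits (placebo-drug).** The range for mixed splits reflects the order of events.

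| Split | Log-rank p | Fisher exact p |
|---|---|---|
| 2-0 | 0.045 | 0.110 |
| 3-0 | 0.014 | 0.036 |
| 4-0 | 0.0043 | 0.0117 |
| 4-1 | 0.024 to 0.026 | 0.043 |
| 5-1 | 0.0080 to 0.0087 | 0.0166 |

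At 0.05 only the 2-0 row changes verdict. At the Protocol's 1% level, 4-0 and 5-1 change instead.

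**Direction of the error.** I enumerated every order of events under no effect. Given exactly two fractures, the nominal 5% test rejects 11% of the time. With seven or fewer fractures it cannot reach 0.05 against the drug: 0-7 gives p = 0.059. The rejection rates, averaged over a binomial number of fractures, are:

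| Assumed risk | Favouring drug | Against drug | Two-sided total |
|---|---|---|---|
| 1% | 4.1% | 0.01% | 4.1% |
| 2% | 3.6% | 0.2% | 3.8% |
| 3% | 3.0% | 0.9% | 3.9% |

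An even split of a 5% test would be 2.5% on each side.

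**Chance that the hazard ratio cannot be estimated.** At least one arm has no fracture with probability 1 − (1 − (1 − r)^75)(1 − (1 − r)^150).

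- r = 1%: 1 − (1 − 0.4706)(1 − 0.2215) = 59%. This includes 0.99^225 = 10% with no fracture in either arm.
- r = 2%: 1 − (1 − 0.2198)(1 − 0.0483) = 26%.
- r = 3%: 1 − (1 − 0.1018)(1 − 0.0104) = 11%.

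**The case against.** The strongest reply is that little depends on this p-value. The SAP calls the analysis exploratory, and fractures lie outside the fixed sequence. Crude and Kaplan-Meier incidences will also be reported, so a reader will see how few events there are. That stands, and it sets the weight of the point.

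A reader might infer that the plan inflates the type I error. It does not do so overall: averaged over event counts, the two-sided rate is 2.6% at a 0.5% risk and about 4% at 1% to 3%. The plan sets no separate limit for each side. What remains is the imbalance between sides and the 11% rate when there are exactly two fractures.

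A reader might also take the 2-0 example as typical. It is not. Up to 12 fractures in total, the log-rank and Fisher verdicts at 0.05 differ only at 2-0 and 6-3 in favour of the drug and 0-8 against it. Under no effect, a 2-0 split has probability 3.0%, 1.2% and 0.3% at risks of 1%, 2% and 3%.

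Finally, Fisher's test is not an error-free standard. It is conservative here, with an actual size of 1.1%, 2.4% and 2.8% at those risks, and it ignores follow-up time. This is a real cost of the change. It does not answer the missing rule for an arm with no event.

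**Conclusion.** The point holds as a modest one. If the 12-month fracture risk is about 1% to 3%, the planned log-rank p-value is too small for sparse splits favouring the drug. Its error falls mainly on that side, and the planned hazard ratio has no finite, usable estimate in roughly one trial in nine to three in five. The change of verdict at 0.05 is essentially confined to the 2-0 split.

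The risk range is an assumption. It would be going too far to say that only a handful of fractures can occur: at a 5% risk about 11 would be expected (225 × 0.05), and the problem shrinks as events accumulate. Nor do the documents support reading this as a threat to a confirmatory claim.

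Separately, the two documents disagree on the confidence level for the same hazard ratio (99% in the Protocol, 95% in the SAP), and SAP Section 5 does not list this as a change.

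**What to change.** In SAP 4.3.2 and Protocol 8.4.3:

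1. Take the fracture p-value from an exact (permutation) log-rank test, or from Fisher's exact test when either arm has fewer than five fractures, mirroring the BMD responder rule.
2. Report the difference in crude 12-month incidence with the Newcombe interval that SAP 4.5.6 already uses for hypercalcemia, and keep the Kaplan-Meier curves.
3. Show the hazard ratio only when both arms have at least one fracture, or use a Firth-penalised or profile-likelihood interval. State what is reported otherwise.
4. Settle on one confidence level, 99% or 95%, in both documents.

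The cost is a few sentences and a few lines of code before database lock, with no new data and no effect on the primary analysis. The statistical price is larger, conservative p-values. Fisher's test also discards follow-up time, which the exact log-rank test keeps.

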1. INTRODUCTION

1.1. Background

Human parathyroid hormone (PTH) is a naturally occurring 84 amino acid hormone and is primarily a regulator of calcium homeostasis (Mannstadt et al, 1999). PTH acts directly on bone to increase calcium resorption, on the gastrointestinal system to increase calcium absorption, and on the kidney to increase calcium reabsorption and 1,25-dihydroxyvitamin D production. In turn, PTH levels are tightly regulated by calcium and vitamin D levels. When given intermittently at low doses, PTH has a well-documented anabolic effect on bone, and can increase bone mineral density (BMD) in a number of intact animal models and in osteoporotic subjects (Dempster et al, 1993).

Abaloparatide (marketed as TYMLOS[®] in the United States [US]) is a novel, synthetic, 34 amino acid peptide designed to be a potent and selective activator of the PTH/PTH-related protein (PTHrP) type 1 receptor (PTHR₁) signaling pathway with 41% homology to PTH[1–34]) and 76% homology to human PTHrP[1–34]. Abaloparatide is differentiated from PTH and PTHrP ligands based on its high affinity and > 1,000-fold greater selectivity for the G protein-coupled (RG) vs the non-G protein-coupled (R⁰) conformation of PTHR₁ (Hattersley et al, 2016). Differential PTHR₁-RG binding with abaloparatide results in potent and transient intracellular cyclic adenosine monophosphate (cAMP) signaling. In nonclinical studies, the transient PTHR₁ activation with abaloparatide strongly favors bone anabolism with a limited effect on bone resorption (Makino et al, 2015). Thus, abaloparatide was developed with the expectation that it would be effective at increasing BMD and reducing fracture in individuals with osteoporosis, but with a limited effect on bone resorption and a reduced risk of hypercalcemia.

1.1.1. Disease and Study Drug Background

Osteoporosis is a systemic skeletal disease characterized by low bone mass and microarchitectural deterioration of bone tissue that leads to enhanced fragility and increased risk of fractures (Rizzoli et al, 2001). This disease is characterized by low BMD and fractures. The fractures associated with the greatest morbidity and mortality, as well as economic burden to society, together make up the clinically significant and medically relevant group termed major osteoporotic fractures. In the US, there are an estimated 2 million osteoporotic fractures annually (Litwic et al, 2014). The number of osteoporotic fractures is projected to increase in both men and women by more than 3-fold over the next 50 years as a result of the aging population (WHO 2007).

Although osteoporosis predominantly affects postmenopausal women, approximately 20% of men over the age of 50 years will sustain an osteoporotic-related fracture in their lifetime. In 2005, the total cost of treatment and rehabilitation for fractures in men in the US was \$4.1 billion and this is projected to rise to \$6.8 billion in 2025 (IOF 2014). Most men experience bone loss with aging and low BMD is frequent in older men and a risk factor for fracture. Many different risk factors may contribute to bone loss and fracture risk in men, including most importantly hypogonadism, glucocorticoids, and excessive alcohol use (Ebeling 2008). Additionally, some men develop osteoporosis without apparent cause, so-called idiopathic osteoporosis (Khosla 2008).

Bone remodeling occurs through the action of osteoclasts, which are involved in the resorption of bone followed by the formation of new bone by osteoblasts. In addition to continued use of calcium and vitamin D, the current therapeutic approach to the treatment of osteoporosis through inhibition of bone resorption includes agents such as bisphosphonates (Rosen 2005) or monoclonal antibody denosumab, that inhibits the action of osteoclasts by binding to receptor activator of nuclear factor kappa-B (RANK) ligand. An alternative approach has been to tip the balance between osteoblastic bone formation and osteoclastic resorption through the use of parathyroid hormone receptor modulation using teriparatide (rhPTH[1–34]).

Until recently, teriparatide has been the only approved osteoporosis treatment in which the major mode of action is stimulation of bone formation (anabolic) rather than suppression of bone resorption. The efficacy of teriparatide has important limitations related to its delayed and modest effects on increasing BMD at the total hip and femoral neck, and on decreasing BMD at the distal one-third radius. The increase in cortical porosity that can occur may result in maladaptive effects on cortical bone microarchitecture (Bilezikian 2007). Abaloparatide has been evaluated in a number of nonclinical and clinical studies for its potential as a novel treatment for osteoporosis. Based on the biology of the PTH₁ receptor signaling pathway, abaloparatide is designed to have less resorptive and hypercalcemic effects than PTH, resulting in a greater net anabolic effect. Abaloparatide has recently been approved in the US for the treatment of women with postmenopausal osteoporosis, bisphosphonates, denosumab, and teriparatide have also been approved for the treatment of osteoporosis in men or to increase bone mass in men with osteoporosis.

